Implementing a Combination of Clinical Parameters (Rapid Diagnostic Tests (RDTs), Biomarkers, and Standard of Care Procedures (SoCs)) for the Etiology Diagnoses of Pneumonia in Pediatric Patients to Improve Clinical Management in Indonesia.
Short title
PEER PePPes (INA-201)
Study type
Prospective observational study
Principal investigator
[name], PhD
Co-Principal investigator
RSU Kabupaten Tangerang [name], SpPK [name], SpA
RS An Nisa [name], SpA [name], SpPK
RSUP [name] [name], M.Kes, SpA, PhD [name], MSi.Med, SpA [name], SpA (K) [name], SpMK
RSUD [name], MPH / RSUD Tugurejo [name], M.Kes, SpA, PhD [name], SpA
RS Bhakti Wira Tamtama [name], M.Kes, SpA, PhD [name], SpA
RSUP dr Sardjito [name], SpA(K) [name], SpA(K) [name] [name], M.Sc., Ph.D, Sp.MK(K)
RSA UGM [name], SpA(K) [name] [name], M.Sc, Sp.A(K)
Study objectives
Primary objective To develop an algorithm for the diagnosis of viral and bacterial pathogens in pediatric patients with pneumonia.

Secondary objectives

- To identify the etiologies of pneumonia in children in Indonesia, which are currently unavailable.
- To document outcomes in pediatric patients with pneumonia in Indonesia.
- To evaluate the performance of each rapid point of care test (to detect influenza and viral syncytial viruses, legionella urinary antigen, biomarkers of bacterial infections (C-Reactive Protein (CRP) and Procalcitonin (PCT)), and standard of care procedures (Chest X-ray) compared to the gold standard molecular assays in differentiating virus and bacterial infections.
- To analyze the performance of combined tests in differentiating virus and bacterial infections.
- To provide information regarding updated strains of circulating respiratory viruses and pathogens in children.

Study Population

Hospitalized patients with pneumonia whose ages range from 2 months to 5 years.

Sample size

The total sample is 275 participants.

Study duration

Study will accrue participants **up to September 2019**. Each participant will have follow up visits in a period of 30 days from the enrollment day.

Eligibility criteria

Inclusion criteria

- Pediatric inpatients whose ages range from 2 months to 5 years
- Meet the case definition for pneumonia which is cough **or** fever with at least one other following symptoms:
 - ✓ Shortness of breath
 - ✓ Tachypnea
 - ✓ Grunting
 - ✓ Crackles/rhonchi
 - ✓ Decreased vesicular breath sound
 - ✓ Bronchial breath sound
 - ✓ Chest x-ray consistent with pneumonia
- Comply with all study procedures including to store required specimens for diagnostic testing and archiving.

Exclusion criteria

- Being Hospitalized for more than 24 hours at enrollment
- Having a cancer or history of cancer
- Having a history of long term exposed of steroid (at the minimum of 2 months)
- Having any condition that might interfere with study procedure and compliance (based on clinicians' judgement)

Study Procedures
Participants who meet the inclusion and exclusion criteria will be enrolled and then having a daily follow up for maximum of 13 days' hospitalization. Next follow up will be taken time at day 14 th after hospitalization date, either on ward or polyclinic. The participations will be ended by day 30 th after hospitalization date when the called follow up is done by the Research Assistant (RA).
This study will collect demographic data, medical history, clinical data, treatment, and risk factors of pneumonia. The study also recorded the supporting examination results include but not limited to Complete Blood Count (CBC) results, blood gas analyses result, CRP, PCT, culture result, rapid test for influenza, Respiratory Syncytial Virus (RSV), legionella, and chest X-ray. In order to produce a robust data, this study will conduct the serological and molecular tests at the reference laboratory.
Whole blood, serum, urine, Nasal Pharyngeal Swab (NPS), sputum/induced sputum, and other respiratory specimens (if available) will be collected for storage and testing at enrollment. Any left-over respiratory specimens and/ or plasma on day 2 and 3 of hospitalization will also be collected to be stored. For additional, at day 14 th after hospitalization serum will be processed from 4 mL of blood for archiving and testing at the reference laboratory.

1. BACKGROUND

Pneumonia accounts for an estimated 920,136 fatalities or 16% of all deaths in children under five years of age.⁽¹⁾ Based on Indonesia National Basic Health Survey, period prevalence of pneumonia in children under 5 years is 18.5 per mil.⁽²⁾ The high rate of morbidity in children with pneumonia may be prevented by promoting exclusive breastfeeding, vaccination, and an improved environment, whereas the mortality can be reduced by providing appropriate management including appropriate antibiotic treatment for bacterial infection which is now still very low (30%).⁽¹⁾

Diagnosing pneumonia using current WHO pneumonia diagnostic criteria is challenging as no one clinical feature is sufficient to diagnose pneumonia definitively. To improve diagnostic performance, a combination of clinical features has to be used.⁽³⁾ Chest X-rays are neither sensitive nor specific. Radiological findings lag behind clinical findings and are unable to differentiate between viral and bacterial etiologies of pneumonia. Differentiation between viral and bacterial pathogens is becoming more important since the introduction of Hib and pneumococcal vaccines that may shift the substantial causes of pneumonia to viruses.⁽³⁾ This distinction is also important for guiding appropriate antibiotic treatment.⁽⁴⁾ The gold-standard for microbiological pathogen assays require specimens that are difficult to collect such as

nasopharyngeal wash or bronchoalveolar lavage and may need several days for the results to be available.

Considering all the factors above, a combination of rapid diagnostic and biomarker tests, using non-invasive or relatively easily collected specimens, and standard of care procedures may help to differentiate between viral and bacterial pneumonia to better guide management (antiviral vs antibacterial treatment).

2. RESEARCH BENEFITS

This study will provide the data and algorithm to differentiating bacterial and viral pneumonia. This algorithm will be useful to transform the management of pneumonia cases and to determine the prevention strategies as well. Other benefit from this study is to obtain a better understanding of pathogen caused by pneumonia to provide the evidence that might change a clinical pathway, for example, for example, the identification of influenza or other viruses as the causes of pneumonia may have an impact on the perceptions of clinicians and health policy makers that these viruses may also cause severe illness and therefore antiviral should be provided. The importance of viral pathogens as the cause of pneumonia will also have an impact on the risk of nosocomial infection and the need of vaccination to health care workers and children. Thus, better understanding of identified pathogens, particularly the newly reported may bring us to new strains invention. Those benefits hopefully will give us the evidence to advice the policy maker, hospital management, and to increase the clinician awareness.

3. OBJECTIVE

3.1. Primary Objective

To develop an algorithm for the diagnosis of viral and bacterial pathogens in pediatric patients with pneumonia.

3.2. Secondary Objectives

- To identify the etiologies of pneumonia in children in Indonesia, which are currently unavailable.
- To document outcomes in pediatric patients with pneumonia in Indonesia.
- To evaluate the performance of each rapid point of care test (to detect influenza and viral syncytial viruses, legionella urinary antigen, biomarkers of bacterial infections (CRP and PCT), and standard of care procedures (Chest X-ray, O₂ saturation, CBC, blood Gas Analyses (if available) compared to the gold standard molecular assays in differentiating virus and bacterial infections.
- To analyze the performance of combined tests in differentiating virus and bacterial infections.
- To provide information regarding updated strains of circulating respiratory viruses and pathogens in children.

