4.3. Type and Design of Study

This study is an observational study, conducted at the pediatric department at three hospitals in Indonesia. It will recruit hospitalized children aged between 2 months to 5 years who meet the inclusion and exclusion criteria. Participants will be followed up for maximum 13 days' hospitalization. At day 14th after hospitalization date each participant will be assessed for his/her symptoms, clinical data, clinical outcome, and serum specimen collection. The end of their participation will be ended on day 30th after hospitalization date, after followed up phone from RA.

Laboratory test procedures will be conducted during the study and/or after study completion. Chest X-Ray, CBC, blood and respiratory specimen cultures including antibiotic resistance test will be performed either as part of standard of care or study addition. Rapid tests for Influenza A and B; Respiratory Syncytial Virus (RSV); and Legionella will be performed as study requirement. C-reactive protein (CRP) and Procalcitonin (PCT) will also be measured for study interest. Molecular assays to identify bacterial and viral pathogens and serological assays to detect infections of several viruses and bacteria will be conducted at the reference laboratory. Any left-over respiratory specimens and/or plasma from day 2 and 3 hospitalization will be stored for archiving.

Specimen that will be stored for archiving, will be maintained for further laboratory testing for up to 5 years after the study is completed. After 5 years, with the decision of Steering

Committee and Governing Board, specimens in the INA-RESPOND specimen repository in NIH RD Jakarta, will either be destroyed, or after IRB approval, transferred to another existing protocol or a repository.

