4.4. Population and Sample Size

This is a preliminary study to characterize the pathogens present in this cohort. The number of participants' that will be enrolled is based on the number of pneumonia cases in 5 years old children or less. This study plan to enroll with total of 275 participants.

With 275 participants, the 95% confidence interval for the prevalence of each pathogen will be no greater than $\pm 7\%$. The study is not powered to test the diagnostic accuracy of the algorithm. The algorithm developed from this study will be evaluated in a larger study, powered to estimate sensitivity and specificity. As a result, no formal power calculations have been provided.

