4.5. Eligibility Criteria

4.5.1. Inclusion criteria

- Pediatric inpatients whose ages range from 2 months to 5 years.
- Meet the case definition for pneumonia which is cough or fever with at least one other following symptoms:
 - ✓ Shortness of breath, marked by at least one of the following signs: head bobbing; nasal flaring; chest indrawing or intercostal retracting.
 - ✓ Tachypnea (RR ≥ 40 /minute, for children 1 to 5 years old, and RR ≥ 50 /minute, for children 2 to 12 months old)
 - ✓ Grunting
 - ✓ Crackles/rhonchi
 - ✓ Decreased vesicular breath sound
 - ✓ Bronchial breath sound
 - ✓ Chest x-ray consistent with pneumonia
- Comply with all study procedures including to store required specimens for diagnostic testing and archiving.

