3.6.7. Laboratory procedures for Molecular and Serological Testing

This study will carry out molecular and serological testing that will be done at the reference laboratory. The study will cover all the costs of those tests.

Table 1 and Table 2 will furtherly explain the required specimen volume and tests needed. Also see appendix A for the work flow.

Table 1. The research specimen and laboratory testing

Visit /Time	Collected Specimen	Amount	Laboratory Testing at	
			Hospital	Reference Lab
Enrollment (up to 24 hours after enrollment)	Whole Blood	2 x 1 ml – 2 ml blood 1 x 3 ml blood	Blood culture (2 sides) CBC	PCR (Streptococcus pneumonia, Staphylococcus aureus, Haemophilus influenza)
	Serum	1 x 4 ml blood	CRP, Procalcitonin, HIV (can be done up to 5 days after enrollment)	Serology IgM and IgG (Influenza A, B, RSV, Parainfluenza virus, Adenovirus, Mycoplasma pneumonia, Chlamydia pneumonia, Bordetella pertussis, Legionella pneumonia)
Enrollment (up to 48 hours after enrollment)	Urine	1 ml – 3 ml urine	Rapid test Legionella antigen	PCR (Legionella pneumoniae, Leptospira)
	Nasopharyngeal swab	2 VTM (1.5 ml)	Rapid test Influenza Rapid test RSV	PCR (18- Viral Panel)
	Sputum/induced sputum	2 ml	Culture, MTB (genexpert, if AFB positive)	PCR (11 Bacterial and 18 viral panel)
	Other resp specimen (leftover – effusi pleura, BAL)	If available	Culture, MTB (genexpert, if AFB positive)	PCR (11 Bacterial and 18 viral panel)
Daily study visit during hospitalization	Left-over respiratory specimen and/or plasma (Daily study visit day 1 & 2 (day 2 & 3 of hospitalization)	If available	None	TBD
Study Visit Day 14th after hospitalization	Serum	4 ml blood	None	Serology IgM and IgG (Influenza A, B, RSV, Parainfluenza virus, Adenovirus, Mycoplasma pneumonia, Chlamydia pneumonia, Bordetella pertussis, Legionella pneumonia)
Follow-up Day 30 th after hospitalization	None	None	None	None

NOTE: Maximum amount of blood drawn in pediatric patients weight 7.3 – 45.5 kgs is 10 ml - 30 ml at any one time or 60 ml – 350 ml cumulative during hospitalization or maximum 1 month (Garza D, Becan-McBride K).

Table 2. PCR Panel for Bacterial & Viral Pathogens

PCR Viral Panel	PCR Bacterial Panel
Human Influenza A virus	Haemophilus influenza
Human Influenza B virus	Streptococcus pneumoniae
Adenovirus	Legionella pneumoniae
Enterovirus	Mycoplasma pneumoniae
Respiratory Syncytial Virus A	Chlamydia pneumoniae

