6.2. Analysis

An interim analysis will be conducted every 3-6 months to discuss the operation and challenges of the screening and enrollment process, the collection of data and specimens, and to analyze the results of bacterial culture, biomarkers, rapid diagnostic tests, molecular and serogical assays.

It is expected that the gold standard measurements will fall into three categories: confirmed viral (33%), confirmed bacterial (20%), and mixed/unconfirmed (47%). For purposes of algorithm development and assessment, we will combine the latter two groups (confirmed bacterial and mixed/unconfirmed) into a single group. The justification for the grouping is that clinically, a patient who receives a mixed/unconfirmed diagnosis will likely be treated in the same manner as a patient with a confirmed bacterial diagnosis.

As this is a preliminary study, we will fit the data using a variety of different approaches for combining diagnostic tests, including classification and regression trees, random forests, and multivariate logistic regression. For models with binary outputs, we will calculate the sensitivity and specificity (defined using confirmed bacterial as "cases" and confirmed viral as "controls"). For models with continuous outputs, we will calculate the receiver operating characteristic (ROC) curve. The relative performance of the models will primarily be evaluated based on sensitivity and specificity. 10-fold cross-validation or similar methods will be used to account for potential over optimism from fitting multiple models.

While clinical relevance is of primary importance, we may also consider algorithms that perform three-category classifications (with the categories as originally defined), as such results may be of etiologic interest. Furthermore, for all analyses, we may consider calculating the positive predictive value (PPV) and negative predictive value (NPV); while sensitivity and specificity are of primary importance, PPV and NPV may provide further useful descriptive information.

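### With pneumonia cases only, respiratory PCR shows which pathogens are present, not which caused the illness, so the etiology objective promises more than the design can estimate

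*Combined protocol and SAP*

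**What the plan says.** **Target.** The first secondary objective (section 3.2, repeated in the Research Summary) is "To identify the etiologies of pneumonia in children in Indonesia, which are currently unavailable". Section 2 expects the findings to show viruses as causes and so to influence clinicians and policy makers. Section 4.4 is narrower: "This is a preliminary study to characterize the pathogens present in this cohort". It continues "This study plan to enroll with total of 275 participants", so that "the 95% confidence interval for the prevalence of each pathogen will be no greater than" ±7%.

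**Population.** Section 4.3 says "It will recruit hospitalized children aged between 2 months to 5 years who meet the inclusion and exclusion criteria", and section 4.5.1 requires that every child "Meet the case definition for pneumonia which is cough or fever with at least one other following symptoms". No children without pneumonia are described. The controls named in section 6.2 are confirmed viral pneumonia cases.

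**Specimens.** In Table 1 (section 3.6.7) the nasopharyngeal swab gets the 18-virus panel only. Sputum or induced sputum, and leftover pleural effusion or lavage, get "PCR (11 Bacterial and 18 viral panel"). Table 1 also lists two blood cultures, blood PCR for three bacteria, Legionella urine antigen, urine PCR, and IgM/IgG serology at enrollment and day 14. Section 3.6.5 makes the day-14 procedures conditional on availability.

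**Labels.** Section 6.2 states: "It is expected that the gold standard measurements will fall into three categories: confirmed viral (33%), confirmed bacterial (20%), and mixed/unconfirmed (47"%). For algorithm development it pools confirmed bacterial with mixed/unconfirmed. For sensitivity and specificity it uses confirmed bacterial as cases and confirmed viral as controls. No readable text says how specimen types or assays are weighted in reaching a confirmed label.

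**The concern.** An organism found in a swab or in sputum may have caused the pneumonia, may be there without causing disease, or may remain from an earlier infection. Separating these needs a background detection rate in comparable children without pneumonia, or evidence from a specimen where a positive result is more specific for cause. The design does not supply the first and supplies the second for only some children and some organisms.

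Two things are at stake. The etiology table could list incidental detections as causes, and section 2 intends those findings for policy use. The algorithm's reference labels could also be affected, if respiratory PCR alone is allowed to set them. A child with viral pneumonia and an incidental bacterium could become mixed, and an otherwise unconfirmed child with an incidental virus could become a confirmed viral control.

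**Working it through.** **1. The plan's precision figure.** Inputs from section 4.4: n = 275, 95% confidence. The worst case is p = 0.5: 1.96 × √(0.5 × 0.5 / 275) = 0.059, or ±5.9 points. Exact (Clopper-Pearson) limits at 138/275 give ±6.1 points. The stated bound of ±7% is true.

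**2. What that bound covers.** Let D be the detection rate in cases and c the background detection rate, independent of cause. The proportion of cases attributable to the organism is (D − c)/(1 − c). The documents give neither value, so these are assumptions. For D = 30%, the sampling half-width is 1.96 × √(0.3 × 0.7 / 275) = 5.4 points. The attributable proportion is:

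- c = 0: 30%
- c = 10%: 0.20/0.90 = 22.2%
- c = 20%: 0.10/0.80 = 12.5%
- c = 30%: 0%

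The uncertainty about cause runs from 0 to 30%. The interval around D does not reflect it, and a cases-only sample cannot estimate c.

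**3. Incidental positives across a wide panel.** Assume one independent incidental rate r for every target. The chance of at least one is 1 − (1 − r)^k, with k = 18 viruses or k = 11 bacteria (Table 2).

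| r | any incidental virus (k = 18) | any incidental bacterium (k = 11) |
|---|---|---|
| 1% | 1 − 0.8345 = 16.55%, about 17% | 1 − 0.8953 = 10.47%, about 10% |
| 2% | 1 − 0.6951 = 30.49%, about 30% | 1 − 0.8007 = 19.93%, about 20% |
| 3% | 1 − 0.5780 = 42.20%, about 42% | 1 − 0.7153 = 28.47%, about 28% |

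The bacterial column applies only where sputum or another respiratory specimen was obtained, because the swab is not tested for bacteria.

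**4. Relation to the expected 33% and 20%.** The classes in section 6.2 are exclusive, whereas the table gives any-positive rates. At r = 2%, virus-only is 0.3049 × 0.8007 = 24% and bacterium-only is 0.1993 × 0.6951 = 14%. The two sets of figures should not be matched.

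**5. How far the other tests reach.** Table 1 serology covers influenza A and B (2 targets), RSV A and B (2), parainfluenza 1–4 (4) and adenovirus (1), which is 9 of 18. The other nine (enterovirus, metapneumovirus, rhinovirus, four coronaviruses, parechovirus, bocavirus) have none. For them, evidence comes from respiratory PCR unless pleural fluid happens to be available. Blood PCR covers three bacteria, and section 4.6.2 allows blood culture after antibiotics.

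**6. Which label changes matter in section 6.2.** Expected counts are 0.33 × 275 ≈ 91 viral, 0.20 × 275 = 55 bacterial and 0.47 × 275 ≈ 129 mixed/unconfirmed.

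| Move | Two-group fit | Scoring |
|---|---|---|
| Confirmed bacterial to unconfirmed | Unchanged (same pooled group) | Fewer cases for sensitivity |
| Mixed to viral | Changed (crosses the boundary) | Follows from the changed fit |

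**The case against.** The strongest reply is that the plan is already modest. Section 4.4 calls it preliminary, speaks of pathogens present and leaves diagnostic accuracy to a larger study; section 10.7 calls it a pilot. It does not rely on airway PCR alone, and it keeps a mixed/unconfirmed class expected to hold 47% of children. This stands as far as it goes. It shows that the estimable target is already written down, but not in the objective or in section 2.

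Three stronger readings are tempting, and the documents do not support them.

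- A reader might infer that respiratory PCR alone makes a child confirmed. Section 6.2 names no assay for its gold standard. The phrase about molecular assays as gold standard is in section 3.2, on the performance of individual tests. A rule may exist in the Manual of Procedures, Figure 1 or the Appendix A work flow, which cannot be seen here. Such a rule would still not supply a background rate.
- A reader might infer that incidental positives could account for the whole expected 33% and 20%. Those are exclusive classes, and the 1–3% rates are assumptions; one uniform rate for all targets is itself a simplification.
- A reader might infer that the study needs a control group to be worthwhile. Detection prevalence, which section 4.4 targets, is estimable without one.

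**Conclusion.** The point holds as a mismatch between claim and design. What can be estimated is the prevalence of each pathogen detected, by specimen type. Sections 3.2 and 2 and the Research Summary promise causes. The ±7% figure is correct but says nothing about attribution. Sterile-site, urine and serological evidence narrows the gap without closing it, since half the viral targets have no serology and the day-14 serum is conditional.

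The size depends on a background rate that the documents do not give. At 1–3% per target, independent and uniform, 17–42% of children would have an incidental virus, and 10–28% of those with a suitable specimen an incidental bacterium. Whether this reaches the algorithm depends on how confirmed is defined, which the readable text does not settle. The point should be corrected, but it is no reason against running a preliminary study.

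**What to change.** 1. Restate the first secondary objective, with matching wording in the Research Summary and section 2, as the prevalence of pathogens detected, by specimen type. Reserve causal wording for detections supported by a normally sterile site (blood, pleural fluid), urine, or serological change between the two sera.
2. Report lavage with the respiratory specimens or separately, not with sterile sites. Table 1 puts it in one row with pleural effusion, so that row needs splitting in the analysis.
3. Add one sensitivity analysis to section 6.2:
   - (a) recompute sensitivity after removing from the confirmed bacterial cases those children whose only bacterial evidence is respiratory PCR;
   - (b) refit the two-group algorithm with children moved to the viral group if they have a viral detection and are mixed only because of a bacterial respiratory PCR;
   - report how many confirmed viral controls rest on respiratory PCR alone.

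Part (b) is needed because part (a) leaves the pooled training group unchanged.

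The cost is wording and one analysis of data already planned; no participants, specimens or control group are added. The downsides are a less favourable etiology claim, fewer confirmed bacterial cases than the expected 55 in the sensitivity analysis, and many viruses reported as detected only.
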